METHODS: Describe the procedures for all aspects of your protocol. Tell us what you are doing.

Participants will be recruited by the Principal Investigator or Study Coordinator from the inpatient and **outpatient** CF population at UAB. Following admission to UAB Hospital for a routine CF exacerbation, **or within the outpatient setting**, the Study Coordinator will discuss the study with participants and obtain written informed consent before initiating the study.

Patients will be randomly allocated in unbalanced numbers (2:1) (n = 15 ketone and n = 8 control) to receive a ketone monoester or an identical-tasting placebo, respectively, for 8 days during the course of hospitalization for treatment of acute pulmonary exacerbation (One, 60 mL bottle of either a ketone ester will be consumed twice daily (30 mL or 15.0 g per dose) (KE4, KetoneAid, Falls Church, VA; 15.0 g or placebo (PL, flavored to closely match taste of the ketone) will be administered following an overnight fast and again at 1500h.

Participants will be **asked to drink about 1 fluid ounce of the ketone or placebo supplement twice a day (once in the morning and once mid-late afternoon) for up to 7 days. Each day in the study, the participant will be asked to fast overnight for about 8 hours before drinking the first dose of ketone or placebo. Following administration of the first dose of either the ketone or placebo and on either day 5, 6, or 7 a small drop of blood will be obtained from their finger before (time 0 min) and 15, 30, 60, 90, and 120 min after drinking the supplement. On days in between visit 1 and visit 2, we will check their blood sugar before drinking the supplement and 30 minutes after they drink the supplement. We will use a commercially available ketone meter (Keto-Mojo, Napa, CA) that provides a rapid assessment of blood ketone and glucose (sugar) levels. The Keto-Mojo device requires a finger stick with a lancet, identical to those used to measure blood sugar, and uses only a small drop of blood. Patients will be educated on how to use the device and self measure ketone and blood sugar.**

Blood sampling will occur from their indwelling catheter or **venipuncture** at day 1 and at day 5, 6, or 7 before administration of the ketone or placebo. We will try to coordinate this with any blood sampling done for clinical care.

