The Keto-Mojo device requires a finger stick with a lancet, identical to those used to measure blood sugar, and uses only a small drop of blood. The device provides values within about 15 seconds following sampling. An alcohol prep will be used to cleanse the surface of the skin prior to each stick and a bandage will be applied to reduce risk of infection.

Participants will remain on all CF chronic care medications **and/or** standard exacerbation therapy (intravenous antibiotics and increased airway clearance throughout the course of the study. The study pharmacist will provide the ketone or placebo supplements by computer-generated random assignment in blocks of three participants and will have sole access to the randomization code.

Spirometry measurements, CRP, and, history/physical exam and Sputum bacteriology will be conducted at the beginning of hospitalization as part of standard of care (these results will be pulled from the medical record for study purposes. Spirometry measurements and history/physical exams will also be performed at the end of hospitalization as part of standard of care and will be pulled from the medical record for study purposes.

For outpatient subjects, these results will be pulled from the medical record and study procedures will also be performed at visit 1 and visit 2 as according to the consent

Spirometry will also be performed in addition to those for standard care just before the participant drinks the ketone supplement or placebo control and one hour after on day 1 and either day 5, 6 or 7.

Additional sputum and blood will be collected at baseline before the treatment and at patient-discharge for trial-specific readouts.

The participants will also be asked to complete the CFQR questionnaire and a food diary every night. They will also be asked to complete the symptom questionnaire on hour after receiving the morning ketone or placebo.

REQUIRED - SELECT ONE OR BOTH: Will this be a retrospective study and/or a prospective study?

Yes No * Retrospective

Yes No * Prospective

Yes No * Will the study involve the prospective collection or analysis of data, documents, or records?

Yes No * Will the study involve the prospective collection or analysis of biospecimens?

What is the expected end date of the study (including data analysis)?

* Provide the total number of subjects to be included at all sites, both retrospectively (including records) and prospectively.

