43. Has your mucus been mostly: Clear, Clear to yellow, Yellowish-green, Green with traces of blood, Don't know

How often during the past two weeks:

- 44. Have you been wheezing?
45. Have you had trouble breathing?
46. Have you woken up during the night because you were coughing?
47. Have you had problems with gas?
48. Have you had diarrhea?
49. Have you had abdominal pain?
50. Have you had eating problems?

Please be sure you have answered all the questions.

THANK YOU FOR YOUR COOPERATION!

Understanding the impact of your child's illness and treatments on his or her everyday life can help your healthcare team keep track of your child's health and adjust his or her treatments. For this reason, we have developed a quality of life questionnaire specifically for parents of children with cystic fibrosis. We thank you for your willingness to complete this questionnaire.

Instructions: The following questions are about the current state of your child's health, as he or she perceives it. This information will allow us to better understand how he or she feels in everyday life. Please answer all the questions. There are no right or wrong answers! If you are not sure how to answer, choose the response that seems closest to your child's situation.

Section I. Demographics

Please fill in the information or check the box indicating your answer.

A. What is your **child's** date of birth?

Date

--	--	--	--	--	--	--	--

Mo Day Year

E. What is **your** date of birth?

Date

--	--	--	--	--	--	--	--

Mo Day Year

B. What is your relationship to the child?

- Mother
- Father
- Grandmother
- Grandfather
- Other relative
- Foster mother
- Foster father
- Other (please describe)

F. What is your current marital status?

- Single/never married
- Married
- Widowed
- Divorced
- Separated
- Remarried
- With a partner

C. Which of the following best describes your child's racial or ethnic background?

- Caucasian
- African American
- Hispanic
- Asian/Oriental or Pacific Islander
- Native American or Native Alaskan
- Other (please describe)
- _____
- Prefer not to answer this question

G. What is the highest grade in school you have completed?

- Some high school or less
- High school diploma/GED
- Vocational school
- Some college
- College degree
- Professional or graduate degree

D. During the **past two weeks**, has your child been on vacation or out of school for reasons **NOT** related to his or her health?

- Yes No

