38. My child wheezed.....				
39. My child had trouble breathing.....				
40. My child woke up during the night because he/she was coughing.....				
41. My child had gas.....				
42. My child had diarrhea.....				
43. My child had abdominal pain				
44. My child has had eating problems				

Please be sure you have answered all the questions.

THANK YOU FOR YOUR COOPERATION!

Appendix 6

EForm Name: IRB EPORTFOLIO

Page: 31. ATTACHMENTS

Section:

Question: Clean Copy

File Name: questionnaire(symtom)220220.docx

SYMPTOM QUESTIONNAIRE**How is your general health today?** (Please check one box)

Very Good
 Good
 Fair
 Poor

Please record any symptoms you may have had today (tick one box for each symptom experienced)

Absent *I did not have this symptom at all*
 Mild *I had this symptom occasionally, but it didn't really bother me*
 Moderate *I had this symptom often, it bothered me quite a bit*
 Severe *I had this symptom very often, it bothered me a great deal*

	Absent	Mild	Moderate	Severe
Nausea				
Vomiting				
Heartburn				
Stomach Pain				
Diarrhea				
Constipation				
Bloating/Feeling of Fullness				

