Belching				

If you experienced any of the above symptoms, at what point after supplementation did they occur?

	Immediately	One hour	Two hours	Three or more hours
Nausea				
Vomiting				
Heartburn				
Stomach Pain				
Diarrhea				
Constipation				
Bloating/Feeling of Fullness				
Belching				

If you experienced any of the above symptoms, how long did they last? If applicable, please specify the number of times the symptom occurred.

	Less than 30 min	One hour	Two hours	Three or more hours
Nausea				
Vomiting				
Heartburn				
Stomach Pain				
Diarrhea				
Constipation				
Bloating/Feeling of Fullness				
Belching				

Final Day Question (only). Which study condition do you think you were in?

- Placebo condition (I **did not** drink the ketones)
- Ketone Condition (I **did** drink the ketones)

Additional Comments:

Appendix 7

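### The symptom questionnaire is timed one hour after the morning dose, too early for its own two-hour and longer answers, and it never reaches the afternoon dose

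*Protocol*

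**What the plan says.** Section 1 (General Questions, Methods) gives one completion time for the symptom questionnaire: participants are "asked to complete the symptom questionnaire on hour after receiving the morning ketone or placebo". The same section sets two doses a day. One sentence says the product "will be administered following an overnight fast and again at 1500h"; another says "once in the morning and once mid-late afternoon".

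The form is reproduced in Appendix 6. It opens with "Please record any symptoms you may have had today" and grades eight gastrointestinal symptoms from absent to severe. It then asks "at what point after supplementation did they occur", with four answers: immediately, one hour, two hours, three or more hours. Next it asks "how long did they last", again with four answers: under 30 minutes, one hour, two hours, three or more hours. There is no answer for a symptom that is still present.

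Section 26 (Risks) expects side effects that can persist for up to a few hours. Tolerability is part of the purpose in section 1 and a hypothesis in the Introduction of the data safety monitoring plan (Appendix 9). Section 9 plans descriptive statistics for it.

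**The concern.** The completion time and the form do not fit each other. The form is built to describe a whole day and to place symptoms up to three or more hours after a dose, but the Methods close it after one hour. Followed as written, it is likely to under-record symptoms that start late, last long or follow the afternoon dose. The study wants to say that the supplement is well tolerated, and this form is the only graded, dose-linked symptom instrument it describes. The preliminary results in section 2 already report good tolerance without adverse effects, and do not say which instrument or time window supports that statement.

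**Working it through.** No sample size, power or error rate is involved. The check sets the timing sentence against the form and the dosing schedule.

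**1. Completion time.** The printed word before hour is taken as a slip for one, since the spirometry sentence in the same section uses one hour. Reading it as an hour gives the same result. The section does not say that the form is daily, but Appendix 6 reserves one question for the final day, which implies repeated use.

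**2. Onset answers that can be true at 1 hour, for that dose.**
- Immediately: yes.
- One hour: yes.
- Two hours: no.
- Three or more hours: no.

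So 2 of 4 are out of reach.

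**3. Duration answers that can be true at 1 hour.**
- Under 30 minutes: yes.
- One hour: only if the symptom began at once.
- Two hours: no.
- Three or more hours: no.

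Again 2 of 4 are out of reach. A symptom still present at completion has an unknown duration and no box to say so.

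**4. Afternoon dose.** It is taken at 1500h or mid-late afternoon, after the form has been completed. The next day's form asks about that day only. The form therefore follows 1 of the 2 daily doses: over 7 days, at most 7 of 14; over 5 days, at most 5 of 10. Nothing in the protocol says that the form stays open, is repeated after the second dose or refers back to the day before.

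**5. Other places where such symptoms could be recorded.**
- *Adverse events.* Appendix 9 collects them daily in both arms and aggregates them by randomized group. Section 26 has them evaluated as they occur, and the Drug Review Sheet has them discussed weekly. No grading scale, time of day or link to a dose is stated.
- *CFQ-R.* Participants are to "complete the CFQR questionnaire and a food diary every night". It has items on gas, diarrhea, abdominal pain and eating problems, but these are asked as "How often during the past two weeks", so they cannot be tied to a dose.
- *Free text.* The form ends with a comments field. The data sheet in Appendix 2 has a comments column at each sampling time up to 120 minutes. Neither is stated to record symptoms.

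None of these is stated to record graded onset or duration by dose.

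**The case against.** The strongest reply is that little depends on this form. No primary outcome, listed secondary outcome or stopping rule uses it, and Appendix 9 calls the tolerability assessment qualitative. Both arms complete it at the same time, so the comparison within the first hour stands. Later symptoms can still be caught as adverse events. All of that is right, and it is why the point is minor. It does not restore onset and duration by dose, which the form asks for and cannot obtain at one hour.

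It can also be said that outpatient procedures follow the consent form, which is not in the copy reviewed and may hold further instructions. That cannot be checked. The Methods text would still need to agree with it.

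A reader might go further and express the loss as a share, dividing the one observed hour by the post-dose hours that the form spans. The documents do not support such a figure. The longest answer is open-ended, so there is no fixed denominator, and nothing says that symptoms spread evenly over the hours after a dose. A reader might also infer that the preliminary statement of good tolerance is wrong, or that the arm comparison is biased. The documents show only that the basis of that statement is not given, and the direction and size of any effect on the arm difference cannot be derived.

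**Conclusion.** The point holds as a minor one. The stated completion time contradicts the form's own recall period and answer options, and leaves the afternoon dose off the form. For the morning dose, 2 of 4 onset and 2 of 4 duration answers cannot be valid. The consequence is confined to what this form can support about tolerability: the first hour after the morning dose. It does not mean that later symptoms go unrecorded, because daily adverse event collection remains. How many symptoms are missed cannot be computed.

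This rests on the Methods sentence being followed literally, on reading its slip as one hour, and on no fuller instruction standing in the consent form.

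**What to change.** Make the completion time in section 1 and the form in Appendix 6 agree.

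**For participants still to be enrolled.** Keep the one-hour entry, so that earlier and later participants stay comparable on it. Reopen the same form at bedtime, with the nightly food diary, to add later symptoms, mark which dose each followed and tick a new still-ongoing box. That box is needed because the latest onset plus the longest duration on the form is at least 3 + 3 = 6 hours, which for a 1500h dose means 2100h or later. Report the one-hour and bedtime entries separately.

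**For participants with only the one-hour form, or if enrolment is closed.** Limit the form-based tolerability conclusion to the first hour after the morning dose. Rest any wider statement, such as the one in section 2, on the adverse event records.

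The second route may be the only one left. Appendix 9 rules out unblinding before recruitment is complete, while section 2 already attributes effects to the ketone ester. If that rule was kept, recruitment had ended, but the enrolment status cannot be read in this copy.

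**Cost.** The bedtime entry means a longer evening form (8 symptoms in three grids, 8 × 3 = 24 entries to revisit, beside the CFQ-R and the diary) and a few hours' recall. It also needs a form and database amendment with IRB approval, and it changes the instrument part-way through the study. Symptoms that start after bedtime would still reach the data only as adverse events. Limiting the conclusion costs one sentence in the report.

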2. CONTINUING REVIEW

Project Information

Starting date of project

Current IRB expiration date

Yes No Do any of the investigators have a financial conflict of interest management plan issued from the Conflict of Interest Review Board?

Indicate the status of your study.

Not yet open

Open

On hold

Closed to enrollment

* Date enrollment closed

On protocol procedure

In long-term follow-up

In data analysis only

Completed

Provide the number of subjects currently active in the study (receiving study intervention, active follow-up, etc.). NOTE: Enter 0 if the study only involves secondary data analysis.

Participant Group/Sub-study/Site	Number acAve

Total number of acAve participants.

Provide the number of subjects **enrolled** since the start of the study by participant groups, sites and/or sub-study. NOTE: Enter 0 if the study only involves secondary data analysis.

Participant Group/Sub-study/Site	Number Enrolled

Total number of participants enrolled since the start of the study

Provide the number of subjects **enrolled** since the last continuing review by participant groups and sub-study.

Participant Group/Sub-study/Site	Number Enrolled Since Last Continuing Review

Total number of participants enrolled since the last continuing review

Yes No Are there preliminary results from the study?

Provide the preliminary results from the study.

Preliminary analysis suggests that patients tolerated the ketone ester well with no adverse effects. We also show that the ketone ester increases circulating ketone concentrations and decreased sputum and some plasma inflammatory markers. There were no significant effects on pulmonary function as measured by spirometry, but patients did report an improvement in their perception of respiratory function as determined by the CFQ-R

Yes No * Has there been any new substantive literature relevant to the risks, procedures, or interventions of the study?

Yes No * Since the last IRB review, has your study received an audit by an internal or external group (e.g., UAB for-cause audit or government entity)? NOTE: This does not include study team self-audit, sponsor monitor visits, or sponsor audits.

Yes No Have there been any changes to the study since the last continuing review? If there has been no continuing review, have there been changes to study activities since the initial review?

Prospective

Have any UAB subjects voluntarily withdrawn or been administratively withdrawn since the last IRB review?

Yes No * Over the life of the protocol, have there been any **Serious Adverse Events (SAEs)/unanticipated problems, and/or unanticipated problems?**

Yes No * Over the life of the protocol, have there been any problems NOT meeting the UAB criteria for reportable problems but the sponsor requests IRB notification?

Yes No * Have there been any protocol deviations since the last IRB approval, including both previously reported and unreported?

Yes No Has there been an IND Annual Report submitted to the FDA since the last approval?

Indicate whether any of the following have occurred since the last IRB Approval.

You have had one or more problems obtaining informed consent.

You have received complaints about the research.

If you wish to add any information for the IRB to consider (e.g., any information the IRB has not already asked for or the research team has not already provided and the research team believes will aid the IRB in their review), provide it here.

Yes No * Is this a multi-site study?

Provide the number of subjects **screened** and **enrolled** at UAB since the last IRB review.

Total screened

Total enrolled

Complete the table for participants who are not of Hispanic or Latino ethnicity.

Racial Categories	Female	Male	Unknown/Not Reported
White			
Black or African American			

Complete the table for participants who are of Hispanic or Latino ethnicity.

Racial Categories	Female	Male	Unknown/Not Reported

Complete the table for participants whose ethnicity is unknown or not reported.

Racial Categories	Female	Male	Unknown/Not Reported	
-------------------	--------	------	----------------------	--

5. RESEARCH DETERMINATION

Research Determination Form

- Yes No * Is the activity a **systematic investigation**?
- Yes No * Is the activity designed to develop or contribute to **generalizable knowledge**?
- Yes No * Does the project involve obtaining information about living individuals?
- Yes No * Does the project involve an **intervention** or an **interaction** with participants?
- Yes No * Does the project involve an FDA regulated test article?
- Yes No * Is the project defined as a **clinical investigation**?

Briefly describe the proposed project, including what materials are being obtained and their sources. **If you provided this information on Page 1 (General Questions), enter "See above."**

Spirometry measurements, CRP, and, history/physical exam and Sputum bacteriology will be conducted at the beginning of hospitalization as part of standard of care (these results will be pulled from the medical record for study purposes. Spirometry measurements and history/physical exams will also be performed at the end of hospitalization as part of standard of care and will be pulled from the medical record for study purposes.

Additional spirometry, questionnaire, sputum and blood will be collected at baseline before the treatment and at patient-discharge for trial-specific readouts for out patients medical history will also be pulled from the medical record

Risk Level - FDA Regulated

* **REQUIRED: Select whether the project involves minimal risk or greater than minimal risk to participants.**
Greater than Minimal Risk

Sources of Private Information

Indicate the information that may be obtained, accessed, used, disclosed, or shared from an individual (living or deceased). Select all that apply.

- An individual's genetic tests
- Genetic tests of family members of a particular individual (including an embryo or fetus)
- Genetic manifestation of a disease or disorder in family members of a particular individual
- Any request for, or receipt of, genetic services, or participation in a clinical study which includes genetic service, by the individual or any family member of the individual
- Education records of an individual
- Alcohol or substance abuse information, including diagnosis, treatment, or referral of treatment for alcohol abuse, substance abuse, or chemical dependency
- Yes No Will the PI or others obtain, review, or make other use of participants' "protected health information" (i.e., information, whether oral or recorded in any form or medium that (a) is created or received by a health care provider and (b) relates to past, present, or future physical or mental health or condition of an individual; or provision of health care; or payment for provision of health care)?
- Identifiable, but not private, information
- Other identifying information
- Yes No * Is the project subject to the 2023 NIH Data Management and Sharing (DMS) policy?
- Yes No * Will information be received from outside of UAB?
- Yes No * Will you share the information with an institution other than UAB?
- Yes No * Will you need to obtain information from a department other than your own?

Provide any additional information for the IRB to consider. Upload any relevant files in the Attachments section.

